## 9.6. Prior Treatment for Psoriasis

Prior systemic treatment for psoriasis is collected from the eCRF page “Prior Systemic Treatment for Psoriasis”. The medications will be coded using WHO Drug Dictionary version September 2021 or later and summarized by ATC and PT for the Safety Analysis Set.

## 9.7. Extent of Exposure

Treatment duration will be summarized by treatment and overall using the Safety Analysis Set.

Subject data listings of study drug dispensation records will be provided.

Treatment duration (in days) is calculated as the date of the last dose of study drug – the date of the first dose of study drug + 1.

The specific definitions of the first dose and last dose dates of study drug are given below:

- First dose date: The date of the first dose of study drug that is dispensed at Week 0/Visit 2 obtained from the study drug exposure eCRF page.
- Last dose date: The date of the last dose of study drug obtained from the end of treatment eCRF page for subjects who have completed the treatment or discontinued early.

Summary statistics for treatment duration (in days), as well as a frequency summary of treatment duration categories (<7 days, 7 - <14 days, 14 - <28 days, 28 - <56 days, 56 - <84 days, 84 – ≤112 days, > 112 days), will be provided.

## 9.8. Treatment Compliance

As part of the routine recording of the amount of study drug taken by each subject, the numbers of capsules dispensed and returned, as well as the number of planned and actual capsules taken will be recorded at each visit during treatment period, starting at Visit 2.

The overall study drug compliance is collected from eCRF page “Study Drug Accountability”. The derivation is defined as below:

- Overall compliance (percent): calculated as actual number of actual capsules taken / planned number of actual capsules taken x 100%

Treatment compliance will not be calculated for subjects (if existent) who have only the tablet dispensed record at Week 0/Visit 2 and no other drug accountability records. A frequency summary of compliance

This document is confidential.

will also be presented with the following categories: < 70%, 70% - ≤ 85%, 85% - ≤100%, and >100% by treatment group and overall.

This document is confidential.

## 10. Efficacy

Unless otherwise specified, all efficacy analyses will be performed using the FAS. The analysis of the primary efficacy endpoint and selective analysis for the secondary endpoints will also be performed using the PPS.

### 10.1. Primary Efficacy Endpoint and Analysis

The primary efficacy endpoint is the proportion of subjects achieving  $\geq 75\%$  reduction from baseline in the PASI score at Week 16. Baseline is defined as the PASI score on Day 1 pre-dose.

For each ME3183 treatment group, the difference in the proportion of subjects achieving the difference in PASI-75 (ME3183 – placebo) and its 95% confidence interval (CI) will be estimated and tested for superior treatment effect using the Cochran-Mantel-Haenszel (CMH) test with prior receipt of any biologics for psoriasis (bio-naïve vs non-bio-naïve) as adjustment factor at a 1-sided significance level of  $\alpha = 0.025$ .

Analysis will be conducted using observed data at Week 16 only (complete-case analysis). In the presence of missing data, additional sensitivity analysis will be conducted using both LOCF and NRI. Under LOCF, the last non-missing PASI score will be carried forward to Week 16, based on which the subject will be considered as responder or non-responder and summarized accordingly. Under NRI, subjects with missing PASI scores at Week 16 will be considered non-responders.

Subgroup analysis will be carried out stratified by the prior receipt of any biologics for psoriasis (bio-naïve vs non-bio-naïve), where Fisher's exact test will be used instead of CMH for superiority.

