5.4 Study Rationale

This study is designed to assess the efficacy, safety, and tolerability of ME3183 administered orally for 16 weeks in subjects with moderate to severe plaque psoriasis as a proof-of-concept study. Phase 1 studies with ME3183 showed it was safe and generally well tolerated in healthy subjects. This is the first study in the target patient population.

Efficacy will be assessed through a set of validated measures for plaque psoriasis. In addition, PK and [CCI](#) evaluations will be conducted. The results of the study will inform the design and the dosing regimens of the subsequent study.

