7.2 Discussion of Study Design

A double-blind, randomized, placebo-controlled study is considered a gold-standard for conducting any interventional study. This design will minimize bias and provide reference data (ie, data from placebo treatment group) for comparison of the efficacy and safety parameters of the ME3183.

Psoriasis is a chronic immune-mediated inflammatory disorder, which requires a chronic therapy. Primary efficacy assessments of psoriasis clinical studies are usually performed at 12 or 16 weeks after initiation of study treatment. This is therefore considered an acceptable treatment duration to observe a CS response that allows for discriminating among different tested doses of ME3183. Primary evaluations of apremilast, the only PDE4 inhibitor currently approved for psoriasis treatment, were also conducted at week 16. A 16-week Treatment Period was also deemed acceptable for the placebo arm because psoriasis is not a life-threatening disease; in case of unbearable flares, subjects can discontinue early from the study and receive appropriate treatment.

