8.4 Study Withdrawal, Removal, and Replacement of Subjects

Although the importance of completing the entire clinical study will be explained to the subjects, any subject is free to discontinue his/her participation in the study at any time and for whatever

reason, specified or unspecified, and without any prejudice. No constraints are to be imposed on the subject, and when appropriate, a subject may be treated with other conventional therapy when clinically indicated. Investigators or the Sponsor can also withdraw subjects from the clinical study if deemed to be necessary.

If a subject discontinues study treatment and/or is withdrawn from the study for any reason, the study site must immediately notify the Medical Monitor. The date and the reason for study discontinuation must be recorded on the electronic case report form (eCRF). Subjects who do not complete or discontinue early from the study treatment will be asked to return to the study site to complete assessments as indicated in the Schedule of Assessments ([Table 1](#)).

In the event that a subject discontinues prematurely from the study treatment because of a TEAE or serious TEAE, he/she will be followed up until it resolves (returns to normal or Baseline values) or stabilizes, or until it is judged by the investigator to no longer be CS. If a TEAE or SAE is causing a long-term effect and could not be followed until resolution, the reason for not following up any further must be recorded in the source document.

Once a subject is withdrawn from the study, the subject cannot reenter the study.

A subject may voluntarily withdraw or be withdrawn from the study treatment or the study at any time for reasons including, but not limited to, the following:

- progressive disease
- unacceptable toxicity or AE
- QT interval corrected using Fridericia's formula (QTcF) >500 msec
- subject withdrawal of consent: at any time, a subject's participation in the study may be terminated at his/her request or on the basis of the investigator's clinical judgement. The reason for subject withdrawal will be noted in the eCRF
- intercurrent illness: a condition, injury, or disease unrelated to the primary diagnosis that became apparent during treatment and necessitated the subject's termination from the study
- general or specific changes in the subject's condition that renders him/her ineligible for further treatment according to the inclusion/exclusion criteria

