#### 4.3. Determination of Sample Size

No formal sample size calculation was performed.

For the assessment of efficacy and safety of ME3183 in subjects with moderate to severe plaque psoriasis in this proof-of-concept study, approximately 125 eligible subjects will be enrolled. Twenty-five subjects will be randomized to each of the following treatment groups: ME3183 [REDACTED] mg BID, ME3183 [REDACTED] mg QD, ME3183 [REDACTED] mg BID; ME3183 [REDACTED] mg QD, and placebo. The number of planned subjects is considered adequate to assess safety and to provide efficacy estimates for in this Phase 2a study. The expected drop-out rate is assumed to be 10%.

This document is confidential.

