## 7. Estimands

### 7.1. Estimand for Primary Efficacy Endpoint

The main estimand for the primary efficacy endpoint 'proportion of subjects achieving  $\geq 75\%$  reduction from baseline in the PASI score (PASI-75) at Week 16' is defined as follows:

- Population: Subjects with moderate to severe plaque psoriasis defined by the study inclusion/exclusion criteria in [Section 4.2](#). The analysis population for the primary efficacy endpoint will be full analysis set as defined in [Section 6.2](#) and per protocol set as defined in [Section 6.3](#).
- Variable: Binary variable indicating whether the subject has achieved  $\geq 75\%$  reduction from baseline in the PASI score (PASI-75) at Week 16.
- Population-level summary: Numbers and proportions of subjects achieving  $\geq 75\%$  reduction from baseline in the PASI score (PASI-75) at Week 16, and differences in these proportions between each ME3183 treatment group and placebo group.
- Intercurrent events:
  - Withdrawals or early terminations will be handled using hypothetical strategy, where Last Observation Carried Forward (LOCF) and Non-responder Imputation (NRI) will be applied as sensitivity analyses in addition to complete-case analysis.
  - All other intercurrent events will be handled using treatment policy strategy.

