Descriptive statistics for the continuous secondary endpoints described above will be provided at each schedule visit by treatment group. Additionally, the secondary continuous efficacy endpoints (including percent changes for PASI, changes for DLQI, BSA and NRS) will be analyzed using a mixed-effect model for repeated measures (MMRM) with the change or percent change from baseline as the response variable, treatment group, visit, treatment-by-visit interaction as fixed effects, and the baseline value as a covariate. An unstructured covariance matrix will be used to model the correlation among repeated measurements. The Kenward-Roger adjustment will be used with restricted maximum likelihood (REML) to make proper statistical inference. The LS mean differences between ME3183 treatment groups and placebo at each scheduled visits along with the 2-sided 95% CIs and 2-sided p-values will be estimated from the MMRM model. In the event that MMRM with unstructured covariance matrix fails to converge, alternative covariance structures will be explored, including Toeplitz, heterogeneous Toeplitz, variance components, compound symmetry, heterogeneous compound symmetry, autoregressive and heterogeneous autoregressive covariance matrices, where the optimal covariance matrix structure will be selected based on Akaike's Information Criteria (AIC), where smaller values of AIC indicate better overall fit. MMRMs will be estimated for the secondary continuous efficacy endpoints using complete case analysis only.

Kaplan-Meier method will be used for summarizing the time to the first response of PASI-50 and PASI-75 in days. The time to the first response of PASI-50 and PASI-75 is defined as the number of days from the first dose of the study drug to the first response. If a subject does not achieve PASI-50 and PASI-75, the variable will be censored on the last PASI assessment date. Median time to response and 95% CI will be provided, when estimable. The CI will be based on log-log transformation. The reverse Kaplan-Meier plots of PASI-50 and PASI-75 will be presented by treatment group. The comparison of the time to PASI-50 and PASI-75 between each ME3183 treatment group and placebo will be performed using the log-rank test.

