### 11.3. Presentation of Concentration Data

#### 11.3.1. Handling of Missing Data

Missing concentration data for all subjects who are administered study drug will be considered as non-informative missing and will not be imputed. No concentration estimates will be provided for missing sample values.

For individual plasma concentration vs. time curves, the following rules will apply:

- Concentration values below the limit of quantification (BLQ) of the corresponding analyte (ME3183 or CCI [REDACTED]) in samples will be treated as zero, with the exception of calculation of geometric mean and geometric coefficient of variation% (CV%), for which these assessments will be excluded.

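### The primary PASI-75 analysis is complete case under a hypothetical strategy with no stated missing-data assumption, and an early-termination PASI filed under Visit 8 would count as Week 16

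*SAP*

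**What the plan says.** **Primary analysis.** SAP 10.1 compares each ME3183 group with placebo by a CMH test stratified on prior biologic use, one-sided 0.025. On missing data it says: "Analysis will be conducted using observed data at Week 16 only (complete-case analysis". LOCF and NRI are sensitivity analyses, and NRI applies only to subjects whose Week 16 PASI is missing.

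**Estimand.** SAP 7.1: "Withdrawals or early terminations will be handled using hypothetical strategy". It names complete case, LOCF and NRI as the analyses, so 7.1 and 10.1 agree with each other.

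**Other PASI analyses.** SAP 10.2 plans an MMRM of PASI percent change and a time-to-PASI-75 analysis. It adds: "MMRMs will be estimated for the secondary continuous efficacy endpoints using complete case analysis only".

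**Missingness assumption.** The SAP gives one only for PK concentrations (11.3.1), which "will be considered as non-informative missing and will not be imputed". It gives none for PASI.

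**Early termination.** Protocol 7.4 has all Visit 8 data collected when a subject stops early. Footnote a of Table 1 makes the Visit 8 (Week 16) column serve also as the Early Termination Visit. SAP 8.4 uses the visit label in the database and plans no re-assignment by date.

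**Dropout.** SAP 4.3: "The expected drop-out rate is assumed to be 10" per cent. It is not split by arm.

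**The concern.** A hypothetical strategy asks what dropouts' Week 16 response would have been had they stayed. Complete case answers that by letting completers of the same arm and stratum stand in for them. Some of the exits the protocol foresees make this doubtful. Protocol 8.4 lists progressive disease and "unacceptable toxicity or AE", and Protocol 7.2 says that "in case of unbearable flares, subjects can discontinue early from the study and receive appropriate treatment".

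The other planned analyses do not fill the gap. LOCF and NRI insert a fixed value. The MMRM does use dropouts' earlier visits, if complete case there means no imputation, but it estimates mean percent change. Time to PASI-75 uses earlier visits but does not estimate Week 16 response.

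The visit label is a separate problem. If a PASI taken at a Week 3 exit is stored as Visit 8, SAP 8.4 makes it the Week 16 result. That subject is then not missing, so complete case, LOCF and NRI all return the same value and the sensitivity analyses test nothing for that subject.

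With 25 subjects per arm, a few exits can decide a comparison, and Protocol 5.4 says: "The results of the study will inform the design and the dosing regimens of the subsequent study".

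**Working it through.** **Inputs from the documents.** 25 per arm and 10% dropout give 25 × 0.9 = 22.5 expected completers per arm. There is no power figure or assumed response to reproduce. Response rates and dropout by arm below are assumptions, with dropout written active/placebo.

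**1. Bias formula.** With dropout share d, completer response rC and dropouts' hypothetical response rD:

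bias = d_A(rC_A − rD_A) − d_P(rC_P − rD_P)

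This is zero if rC = rD in each arm, or if the two terms cancel.

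**2. Outer bound: every dropout a non-responder, true response 30% vs 8% (22.0 points).** Complete case gives:
- 10%/10%: 30/0.9 − 8/0.9 = 24.4
- 20%/5%: 30/0.8 − 8/0.95 = 29.1
- 5%/20%: 30/0.95 − 8/0.8 = 21.6

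**3. Dropout driven by the last observed PASI, same true 22.0 points.** The simulation assumed:
- Percent improvement at Weeks 4, 8, 12 and 16 is normal with SD 30, and earlier means are 50%, 75% and 90% of the Week 16 mean.
- Correlation is 0.6, 0.8 or 0.9 to the power of visits apart.
- Dropout log-odds are 1 or 2 per SD, calibrated to the stated rate in each arm.
- Strata are 16 and 9 per arm, with 40,000 runs in each of the six settings.
- Imputation uses 30 data sets, a pooled Mantel-Haenszel risk difference and a Wald test. The other methods use CMH.

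Ranges are over the six settings. Rejection is with 10% response in both arms (nominal 2.5%).

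| Dropout | Complete case | Imputation | NRI | Rejection, complete case | Rejection, imputation |
|---|---|---|---|---|---|
| 10%/10% | 22.7–24.2 | 22.1–22.2 | 20.4–21.8 | 2.0–2.2% | 2.1–2.4% |
| 20%/5% | 24.1–27.9 | 22.3–22.7 | 18.1–21.1 | 2.9–3.5% | 1.9–2.3% |
| 5%/20% | 21.5–21.7 | 21.7–22.0 | 21.8–22.0 | 1.0–1.3% | 1.8–2.5% |

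At 5%/20%, complete-case power is 40–42%, against 53–54% without dropout; part of that is simply fewer subjects.

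**4. One dropout rule for both arms.** The table forces the rate in each arm. If one PASI-driven rule applies to both arms at 10% overall, dropout comes out at 6–8% active and 12–14% placebo. Complete case then gives 22.2–22.8, a bias of 0.2–0.8 points.

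**5. Whole-number check.** Single stratum, one-sided: z = (a − E)/√V, with E = n₁m/N and V = n₁n₂m(N − m)/[N²(N − 1)]. Take five dropouts, all non-responders, split 4 active to 1 placebo:
- NRI, 7/25 vs 2/25: E = 4.5, V = 1.883, z = 1.82, p = 0.034
- Complete case, 7/21 vs 2/24: E = 4.2, V = 1.833, z = 2.07, p = 0.019

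The reverse split takes 6/25 vs 1/25 (0.022) to 6/24 vs 1/21 (0.032). A 3-versus-2 split flips neither. Among all tables with at most 6 placebo responders it flips only two: 10/25 vs 4/25 and 9/25 vs 3/25.

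**6. Visit label alone.** Suppose 5 active and 2 placebo subjects leave early as non-responders, with 7 and 2 responders among completers.
- Exit PASI not counted: 7/20 vs 2/23, difference 26.3 points, p = 0.018.
- Exit PASI stored as Visit 8: 7/25 vs 2/25, difference 20.0 points, p = 0.034.

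In simulation with random dropout at 35% vs 5%, a difference of 30.0 becomes 28.4 (10%/10%) or 24.8 (30%/10%) if every exit PASI is stored as Visit 8.

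**The case against.** The case for leaving the plan alone is strong on size.

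- **Forced arm rates.** The 20%/5% row needs active subjects to leave for poor PASI four times as often as placebo. If poor PASI drives exit and the drug works, placebo should lose more. The documented reason for excess active exits is toxicity, and nothing in the documents says those subjects are PASI non-responders. With 20% active dropout unrelated to PASI and 5% efficacy-driven placebo dropout, complete case gives 21.6–21.7 against 22.0.
- **Small against noise.** At 30% vs 8% the standard error is √(0.3 × 0.7/25 + 0.08 × 0.92/25) = 10.7 points.
- **Already probed.** LOCF and NRI tables are planned. If every dropout is a non-responder, NRI is correct at 22.0, while imputation gives 26.6 at 20%/5%.
- **Imputation is favoured by the simulation.** Data come from the normal model the imputer fits, some simulated improvements exceed 100%, and baseline PASI was not simulated.

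All of this stands, and it limits the claim. It does not supply the missing statement of the assumption, an analysis of Week 16 PASI-75 that uses earlier visits, or a safeguard on the visit label.

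A reader might infer three stronger things that the documents do not support:
- **That SAP 7.1 and 10.1 contradict each other.** They agree.
- **That complete case inflates the drug effect or the error rate in general.** At 10%/10%, rejection is 2.0–2.2%, and the flare route makes the test conservative.
- **That exit scores do enter as Week 16, or that no visit rule exists.** SAP 8.4 is a rule. What is unknown is the database label, and the SAP's planned LOCF and NRI suggest that withdrawn subjects were expected to be missing at Week 16.

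**Conclusion.** The point holds as a gap that is cheap to close, not as an error that invalidates the primary analysis. Complete case rests on an unstated assumption about dropouts, and no planned analysis of Week 16 PASI-75 uses their earlier visits under missing at random.

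At the documents' 10% dropout and an assumed 30% vs 8%, the bias is about 0.2–0.8 points under one shared PASI-driven rule and 0.7–2.2 points at a forced 10%/10%. It reaches 2–6 points (7.1 at the outer bound) only if active dropout is well above placebo and driven by poor PASI. If placebo loses more, the test is conservative and loses power. With 25 per arm, a 4-versus-1 split of five dropouts can still move a result across 0.025.

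The visit-label problem follows from the text of Protocol 7.4, Table 1 and SAP 8.4. It bites only if the database stores an exit PASI under Visit 8, which the documents do not show.

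**What to change.** Before unblinding, and keeping the hypothetical estimand:

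1. **SAP 8.4 and 10.1.** State that a PASI taken at an early-termination visit before the Day 113 (±3) window is not a Week 16 observation, even if recorded under Visit 8. Treat it as missing at Week 16 for complete case and NRI. It may be used in LOCF and in imputation.
2. **SAP 10.1.** State the missing-data assumption. Add multiple imputation of Week 16 PASI from baseline PASI, arm, biologic stratum and earlier visits, with PASI-75 derived in each imputed data set. Preferably make this primary; at the least make it a pre-specified sensitivity analysis. Specify the pooled stratified risk difference and how the CMH test is combined or replaced after imputation. Keep complete case, LOCF and NRI.
3. **SAP 14.** Record the change, since Protocol 15.3.1 names the CMH test.

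The cost is SAP wording, one imputation model and one extra set of tables. The PASI visits needed are already collected. Power is about the same: at 35% vs 5% with random 10%/10% dropout, imputation has 81.2% against 79.3% for complete case with the same Wald test (76.0% with CMH). A residual bias remains, up to 0.7 points in the table above and larger if dropouts do worse than their earlier visits predict; NRI continues to probe this.

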15.3.1 Analysis of the Primary Efficacy Endpoint

The primary efficacy endpoint is the proportion of subjects achieving $\geq 75\%$ reduction from Baseline in the PASI score at Week 16. For each ME3183 treatment group, the difference in the proportion of subjects achieving the difference in PASI-75 (ME3183 – placebo) and its 95% confidence interval will be estimated and tested for superior treatment effect using the Cochran-Mantel-Haenszel test at a 1-sided significance level of $\alpha = 0.025$. The PASI score will be reported for each treatment group together with the 95% confidence interval for mean.

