#### 4.4. Treatment Assignment and Blinding

##### 4.4.1. Method of Study Treatment Assignment

Prior to dosing on Day 1, all the eligible subjects will be randomly assigned to 1 of the 5 treatment groups in a 1:1:1:1:1 ratio. Subjects will be assigned a randomization number through interactive web response system (IWRS), in accordance with the randomization code generated by the authorized personnel at PPD [REDACTED] designated by PPD [REDACTED]. An unblinded, independent study statistician will be assigned to produce the randomization schedule. Once a randomization number is allocated to 1 subject, same number may not be assigned to another subject even if the former discontinued the study.

To promote balanced allocation, randomization will be stratified by the subject's receipt (yes/no) of previous treatment with a biologic drug for psoriasis. Bio-naïve subjects will be randomized above 50% of the planned total subject randomization.

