## **8.6. Subgroups**

Selected analysis will be carried out further stratified by prior receipt of any biologics for psoriasis (bio-naïve vs non-bio-naïve, where bio-naïve is defined as not receiving any biologics for psoriasis previously and non-bio-naïve is defined otherwise), including primary efficacy analysis and selective secondary efficacy analysis for PASI scores (actual values, percent change from baseline at post-baseline visits, proportions of subjects achieving PASI-50, PASI-75, PASI-90 and PASI-100 at post-baseline visits).

This document is confidential.

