### 10.2. Secondary Efficacy Endpoints and Analyses

The binary variables for secondary endpoints include the following:

- The proportion of subjects achieving PASI-50, PASI-75, PASI-90, PASI-100 at all visits from Week 1 to Week 16
- The proportion of subjects achieving an sPGA score of "0" ("clear") or "1" ("almost clear") combined with 2-point reduction on the 5-point sPGA scale at all visits from Week 1 to Week 16
- The proportion of subjects with at least a 5-point reduction from baseline in the DLQI score at all visits from Week 1 to Week 16

The binary secondary endpoints will be analyzed using similar methods as described in [Section 10.1](#). Analysis of PASI-related secondary endpoints will be based on both FAS and PPS using complete case analysis, LOCF and NRI. In addition, analysis will be performed stratified by receipt of any biologics for psoriasis based on FAS. Analysis of the secondary endpoint of achieving an sPGA score of "0" ("clear") or "1" ("almost clear") combined with a 2-point reduction on the 5-point sPGA scale will be based on both FAS and PPS using complete analysis, LOCF and NRI. Analysis of the secondary endpoint of at least 5-point reduction from baseline in the DLQI score will be based on both FAS and PPS using complete case analysis only.

The continuous variables for secondary endpoints include the following:

This document is confidential.

- The percent change from baseline in PASI score at all visits from Week 1 to Week 16
- The change from baseline in affected BSA at all visits from Week 1 to Week 16
- The change from baseline in the itch NRS at all visits from Week 1 to Week 16
- The change from baseline in the DLQI score at all visits from Week 1 to Week 16

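### The biologic-history subgroup analysis tests superiority separately within each stratum and plans no comparison of the effect between strata, so it does not answer whether the effect differs by prior biologic use.

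*SAP*

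**What the plan says.** SAP 10.1 compares each regimen with placebo on PASI-75 at Week 16 by a CMH test adjusted for prior biologic use, one-sided at 0.025, and estimates the difference in proportions with a 95% confidence interval. It then adds a subgroup analysis by prior biologic use, "where Fisher's exact test will be used instead of CMH for superiority".

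SAP 8.6 sets the scope: "Selected analysis will be carried out further stratified by prior receipt of any biologics for psoriasis". This covers the primary analysis and the PASI-50/75/90/100 proportions at post-baseline visits. SAP 10.2 repeats it for the PASI-related secondary endpoints: "In addition, analysis will be performed stratified by receipt of any biologics for psoriasis based on FAS". The Index of Tables (SAP 18) lists six stratified Week 16 PASI-75 tables: complete-case, LOCF and NRI, each in the FAS and the PPS.

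On stratum size, SAP 4.4.1 says "Bio-naïve subjects will be randomized above 50% of the planned total subject randomization". Protocol 7.1 adds a sponsor-determined maximum for biologic-experienced subjects and does not give the figure. SAP 4.3 says "Twenty-five subjects will be randomized to each of the following treatment groups".

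The only interaction term in the SAP is treatment-by-visit, in the MMRM of 10.2. There is no treatment-by-biologic-history contrast, no homogeneity test, no minimum stratum size and no statement on how the stratum p-values are to be read.

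**The concern.** A subgroup analysis by biologic history should ask whether the treatment effect differs between bio-naive and experienced subjects. The planned output is two verdicts per regimen, each on whether that stratum alone reaches significance. A difference between the verdicts is not evidence of a difference between the effects: the strata are unequal by design, both are small, and a Fisher test on very few subjects rarely rejects.

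Protocol 5.4 says the results will inform the design and dosing regimens of the subsequent study. Biologic history is the only randomisation factor and the only planned subgroup. A table showing significance in bio-naive subjects and none in experienced subjects could therefore influence the next population when the data hold no evidence that the effects differ.

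**Working it through.** **Inputs from the documents.** Five groups of 25, which reproduces the planned total: 5 × 25 = 125. Allocation is equal, as subjects are "randomly assigned to 1 of the 5 treatment groups in a 1:1:1:1:1 ratio". The bio-naive share is above 50%, so the experienced stratum has at most about 12 per arm. The documents state no power or response rate, overall or by stratum, so there is no planned power to reproduce.

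**Assumptions.** One-sided 0.025, stated for CMH and not restated for Fisher, carries over. PASI-75 is 10% on placebo and 50%, 40% or 30% on active, *the same in both strata*. Splits per arm (bio-naive/experienced) are 13/12, 15/10, 18/7 and 20/5.

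**Step 1: power in each stratum.** With n per arm, a responders on active and b on placebo, the Fisher p-value is P(X ≥ a), X hypergeometric with 2n subjects, n on active and a + b responders. Power is the sum of Bin(a; n, p1) × Bin(b; n, p0) over all tables with p ≤ 0.025.

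**Step 2: combine the strata.** They are independent. With powers A (bio-naive) and B (experienced):
- bio-naive only = A(1 − B)
- experienced only = B(1 − A)
- neither = (1 − A)(1 − B)

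Example, 20/5 at 10% vs 50%: A = 0.742, B = 0.121, so bio-naive only = 0.742 × 0.879 = 0.65.

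| Rates | Split | A | B | Bio-naive only | Experienced only | Neither |
|---|---|---|---|---|---|---|
| 10% vs 50% | 13/12 | 0.490 | 0.425 | 28% | 22% | 29% |
| | 15/10 | 0.536 | 0.295 | 38% | 14% | 33% |
| | 18/7 | 0.668 | 0.133 | 58% | 4% | 29% |
| | 20/5 | 0.742 | 0.121 | 65% | 3% | 23% |
| 10% vs 40% | 13/12 | 0.276 | 0.233 | 21% | 17% | 56% |
| | 15/10 | 0.325 | 0.152 | 28% | 10% | 57% |
| | 18/7 | 0.426 | 0.053 | 40% | 3% | 54% |
| | 20/5 | 0.492 | 0.055 | 47% | 3% | 48% |
| 10% vs 30% | 13/12 | 0.116 | 0.095 | 10.5% | 8% | 80% |
| | 15/10 | 0.149 | 0.057 | 14% | 5% | 80% |
| | 18/7 | 0.205 | 0.015 | 20% | 1% | 78% |
| | 20/5 | 0.242 | 0.019 | 24% | 1% | 74% |

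**Step 3: what the smallest strata can show.** With 3 per arm the smallest possible p is 0.05, so significance is impossible. With 4 per arm only 4/4 vs 0/4 suffices. With 5 per arm the only qualifying results are 4/5 vs 0/5, 5/5 vs 0/5 and 5/5 vs 1/5.

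**Step 4: the between-stratum contrast.** The contrast is the bio-naive risk difference minus the experienced risk difference. Its variance is the sum of p(1 − p)/n over the four cells. With true rates of 10% and 50%, p(1 − p) sums to 0.09 + 0.25 = 0.34 in each stratum, so:
- 13/12: SE = √(0.34/13 + 0.34/12) = 0.233, 95% half-width about 46 percentage points
- 20/5: SE = √(0.34/20 + 0.34/5) = 0.292, half-width about 57 points

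Exact enumeration of a two-sided 0.05 test of this contrast, with one responder and one non-responder added to each cell as a small-sample correction, gives a false signal of different effects in 3.1% to 3.4% of trials per regimen at 10% vs 50% in both strata. If the effect were absent in experienced subjects (10% vs 10%) and 10% vs 50% in bio-naive subjects, it would detect the difference in 38%, 39%, 35% and 28% of trials at 13/12, 15/10, 18/7 and 20/5.

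**The case against.** Five points deserve weight.

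1. **Fisher's test is a sensible choice within a stratum.** The adjustment factor is constant there and counts are small. This stands: the defect is the missing contrast, not the test.
2. **No conclusion in the plan rests on a stratum result.** A reader might infer that the SAP would conclude there is no effect in experienced patients. It has no such rule. The analysis is labelled a subgroup analysis, follows the primary test, and belongs to a proof-of-concept trial with no formal sample size calculation. This stands and limits the severity. Still, the text says superiority and nowhere says descriptive.
3. **Discordant strata are not the expected result in general.** A reader might infer that they are. At 10% vs 40%, neither stratum is significant in 56% of trials at 13/12 and 57% at 15/10. At 10% vs 30%, the strata disagree in only 19% to 25%. Near an even split, the reverse pattern (22%) is almost as likely as bio-naive only (28%), so low power in both strata is the cause there, not unequal size.
4. **Stratum differences with intervals may already be planned.** SAP 10.1 replaces only the CMH test, so a natural reading keeps the difference and its 95% interval. This is plausible but not explicit, and it supplies no between-stratum estimate.
5. **An interaction test has little power here.** This is true, so the estimate and its interval should lead.

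**Conclusion.** The point holds as a minor one. The planned subgroup analysis does not address whether the effect differs by biologic history, because nothing compares the strata.

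With equal true effects of 10% vs 50%, significance in bio-naive subjects only occurs per regimen in about 28% to 65% of trials across splits from 13/12 to 20/5. The range is 21% to 47% at 10% vs 40%, and 10.5% to 24% at 10% vs 30%. A test of the contrast itself would wrongly signal a difference in about 3% to 4%.

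These figures rest on assumed response rates, an assumed split and the carry-over of one-sided 0.025 to Fisher's test; the documents fix none of the three. They take 25 per arm with no missing data. The primary CMH comparison uses both strata with biologic history as adjustment factor, and nothing here weakens it.

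**What to change.** In SAP 8.6 and 10.1, with 10.2 following by reference:

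- Make the main subgroup display, for each regimen, the PASI-75 rates by stratum and the risk difference from placebo by stratum, with small-sample 95% confidence intervals.
- Add for each regimen the between-stratum difference in risk difference with its 95% confidence interval. Any interaction p-value should be on the same scale. An odds-ratio homogeneity test such as Zelen's would answer a different question and has very little power at these sizes.
- Label any retained within-stratum Fisher p-values as descriptive, and state their sidedness.
- State that no superiority or lack-of-effect conclusion is drawn from a single stratum, and that a non-significant interaction does not show equal effects.

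The cost is a few lines of SAP text and some changed columns in the stratified tables; no new data are needed. The drawback is an imprecise contrast: about 28% to 39% power even if the drug did nothing in experienced subjects. The SAP should say so.
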